4.2 Treatment Assignment

Following receipt of signed informed consent from the study subject, completion of baseline assessments at screening and meeting study inclusion and exclusion criteria, the subject will be evaluated by the PI for enrollment eligibility. The Study Manual contains instructions for assigning a randomisation number. The randomisation number will be carefully matched to study drug by a trained member of the Pharmacy team before dispensing study drug. The PI or delegate will maintain a list of contact information for all study participants should additional contact be required. Code-break envelopes will be supplied to the pharmacy if unblinding is required due to a serious or life-threatening adverse event.

4.3 Safety Criteria for Stopping Dosing

Advancing to the next dose cohort will be done after review of safety data by the PI and the Sponsor's Medical Monitor, both of whom are unblinded as to treatment assignment in Part A and blinded as to treatment assignment in Part B. If a dose is safe, then the next dose cohort will be enrolled. Criteria that would result in a pause in active dosing and further investigation by the study team include if any subject experiences a SAE deemed related to the study drug; if two or more subjects experience the same grade 3 or higher AE; if accumulation of SAEs and/or AEs collectively raises a safety concern in the opinion of the investigator, research monitor, or study sponsor; or if any subject experiences an adverse event of special interest (AESI).

If a subject develops a significant allergic reaction or anaphylaxis following study drug administration, the study drug will be immediately discontinued for that subject and no further doses given. The PI should contact the Sponsor's Medical Monitor to determine whether to discontinue study treatment for a given subject. Regardless of communication with the Sponsor, the PI is authorized to discontinue the study drug at any time if it is in the best interest of the safety of the subject. Treatment may also be discontinued at the request of the subject.

4.4 Criteria for Study Termination

Subjects who must discontinue treatment for any reason should continue to complete the study follow-up visits through final study visit. If a subject is not able to comply with study safety monitoring or is significantly non-compliant with study protocol and/or treatment, the PI should inform Lumen Bioscience, Inc. about early termination of the subject's study participation. Criteria for early termination are in the section titled Early Termination of Subjects in this protocol.

5 STUDY POPULATION

Subjects will be required to meet all inclusion criteria to enroll in this study. If any exclusion criteria are met, enrollment will be declined.

5.1 Inclusion Criteria

A subject must fulfill all the following criteria to be eligible for enrollment:

- 1. Male or female between 18 and 50 years, inclusive, at time of informed consent
- 2. Willingness to participate after written informed consent obtained
- 3. Available for all planned clinical visits for physical examinations, blood draws, stool collections
- 4. General good health, without significant medical illness or abnormal physical examination findings as determined by the PI.
- 5. Adequate safety laboratory results, renal and liver function.
 - a. Absolute neutrophil count $\ge 1.5 \times 10^9/L$
 - b. Lymphocyte count < $6.0 \times 10^9/L$
 - c. Platelet count $\ge 150 \times 10^9/L$
 - d. Hemoglobin ≥ 110 g/L
 - e. $eGFR \ge 40 \text{ mL/min/1.73 m}^2$
 - f. ALT and/or AST \leq 3x ULN
 - g. Total bilirubin ≤ 1.5x ULN
 - h. Serum albumin \geq 28 g/L
- 6. Females of childbearing potential should be using and committed to continue using one of the following acceptable birth control methods:
 - a. Sexual abstinence (inactivity) or exclusively same-sex partner for 1 month prior to screening through study completion; or
 - b. IUD in place for at least 1 month prior to study through study completion; or
 - c. Stable hormonal contraception for at least 1 month prior to study through study completion; or
 - d. Surgical sterilization (vasectomy) of male partner at least 6 months prior to study.
- 7. To be considered of non-childbearing potential, females should be surgically sterilized (bilateral tubal ligation, hysterectomy, or bilateral oophorectomy at least 2 months prior to study) or be post-menopausal and at least 12 months since last menses.
- 8. Male participants must use condoms during the study and through study completion.

5.2 Exclusion Criteria

A subject fulfilling any of the following criteria at screening is to be excluded from enrollment in the study:

- 1. Treatment with an experimental compound within 30 days.
- 2. Treatment within 30 days or planned use within the study period with immunomodulator or immunosuppressant agent.
- 3. Pregnancy or breastfeeding.
- 4. Presence of any of the following clinical conditions:
 - a. History of one or more of the following: cardiac insufficiency (NYHA III/IV), uncontrolled cardiac arrhythmias, unstable ischemic heart disease, or uncontrolled hypertension (systolic blood pressure > 170 mmHg or diastolic blood pressure > 110 mmHg).
 - b. History of venous thromboembolic disease within 12 months, myocardial infarction, or cerebrovascular accident.
 - c. Unstable pulmonary, renal, hepatic, endocrine or hematologic disease.
 - d. Gastrointestinal disorder requiring ongoing care by a physician.
 - e. Autoimmune disease, mixed connective tissue disease, scleroderma, polymyositis, or significant systemic involvement secondary to rheumatoid arthritis.
 - f. Evidence of active malignant disease, malignancies diagnosed within the previous 5 years, or breast cancer diagnosed within the previous 5 years (except skin cancers other than melanoma).
 - g. Known active current or history of recurrent bacterial, viral, fungal, mycobacterial or other opportunistic infections, excluding urinary tract infections; or major episode of infection requiring hospitalization or treatment with IV antibiotics within 4 weeks.
 - h. Positive serology for HIV infection or history of other immunodeficiency illness.
 - i. Positive serology results for HBsAg or HCV
 - j. Significant neuromuscular disease or neuropathy
 - k. Psychiatric condition
 - I. Alcohol or illicit drug abuse/dependency or positive urine toxicology screen for drugs of abuse other than marijuana. Alcohol and tobacco consumption are permitted.
 - m. Significant food allergy restrictions.

6 DESCRIPTION OF TREATMENT

6.1 Compound

The study drug, LMN-101, and placebo will be supplied by Lumen Bioscience, Inc. (Seattle, Washington, USA). LMN-101 is VHH-derived binding protein designed to bind and inhibit FlaA (a flagellin filament protein of *Campylobacter jejuni*), delivered in whole, spray-dried, encapsulated spirulina biomass. LMN-101 ingredients are spray-dried spirulina biomass (containing the aa682 protein) and trehalose (NF grade) containing 300 mg or 500 mg of biomass. Placebo consists of wild-type spirulina and trehalose (NF grade) packaged into identical capsules containing 300 mg or 500 mg of biomass.

6.2 Dosing Regimen

Subjects will be sequentially assigned to Part A or Part B.

In Part A, subjects will be assigned to a single dose of 3000 mg PO given as six 500-mg capsules of LMN-101 (2 subjects).

In Part B, subjects will be sequentially assigned to the following dosing regimens and will be randomized within that dose regimen to active or placebo treatment:

- 300 mg PO TID given as a single 300-mg capsule of LMN-101 orally three times daily for 28 days (4 subjects) or identical-appearing placebo capsule (2 subjects).
- 1000 mg PO TID given as two 500-mg capsules of LMN-101 orally three times daily for 28 days (4 subjects) or identical-appearing placebo capsules (2 subjects).
- 3000 mg PO TID given as six 500-mg capsules of LMN-101 orally three times daily for 28 days (4 subjects) or identical-appearing placebo capsules (2 subjects).

All subjects will receive background therapy consistent with the local standard of care. The research pharmacy should label study drug according to the Study Pharmacy Manual and using institutional Standard Operating Procedures.

6.3 Dosage Form

LMN-101 doses are packaged in Vcaps Plus[®] vegetarian capsules (Capsugel, Morristown, NJ, US) or equivalent. Placebo doses are packaged into identical capsules containing 300 mg or 500 mg of biomass. Bulk containers of capsules are provided with a desiccant pouch.

6.4 Timing of Doses

The study drug administration date and start and stop times must be recorded in the subject's chart and in the case report form (CRF). Capsules are to be self-administered by the subject three times daily and may be taken with meals. The subject will be provided a subject diary by the research clinic to record study drug administration, date, time, and relationship to meals.

6.5 Route of Administration

The study drug and placebo must be administered orally and may be taken with fluids or food. For the first dose only, please withhold food for an hour before and after the study drug administration. Please administer the first dose with 240 mL of water.

6.6 Packaging and Labeling

Product labeling states:

LMN-101 Drug Product, 300 mg or 500 mg capsules For oral use only Lot No: Re-test Date: November 2020 Store at 15-25 °C (59-77 °F) Manufactured by Lumen Bioscience, Inc., Seattle, WA 98103 USA [contact] Local Sponsor: Lumen Bioscience Australia Pty Ltd, [name] [name] CAM01 For clinical trial use only Keep out of reach of children

Placebo, wild-type Spirulina platensis, 300 mg or 500 mg capsules

For oral use only Lot No: Re-test Date: November 2020 Store at 15-25 °C (59-77 °F) Manufactured by Lumen Bioscience, Inc., Seattle, WA 98103 USA [contact] Local Sponsor: Lumen Bioscience Australia Pty Ltd, [name] [name] CAM01 For clinical trial use only Keep out of reach of children

6.7 Storage

Capsules containing LMN-101 or placebo should be stored at room temperature, 59° to 77° F (15° to 25° C) and protected from moisture, light, and extreme heat during storage. Capsules contain no preservatives. Any damaged or partially used capsules should be discarded using appropriate drug disposal procedures and documented. To ensure appropriate storage conditions, study drug storage temperatures must be measured and recorded daily. The storage area should restrict access to study personnel only.

For study drug dispensed to the subject, the study drug may be stored at room temperature with a recommendation to protect from moisture, light and extreme heat.

6.8 Study Drug Accountability

The Investigator or delegate will be responsible for implementing a system for documenting drug accountability of clinical supplies at the clinical site in conjunction with the institutional pharmacy. Only pharmacy personnel trained by the Investigator or delegate should receive deliveries. A signature of one of these individuals is required for delivery. Upon receipt of clinical supplies, the trained pharmacy personnel will:

- Confirm (via temperature indicator included in the shipment) that product temperature is within acceptable limits 59° to 77° F (15-25 °C). Document on the receipt form.
- Conduct an inventory of the shipment to verify agreement with the Packing List.
- Acknowledge receipt of the clinical supplies by dated signature of the receipt form.
- Send a copy of the receipt form to Lumen Bioscience or its designee.
- Retain a copy of the receipt for drug accountability records.

6.9 Study Drug Handling and Disposal

Study drug is to be dispensed only to eligible subjects in accordance with the protocol. The Investigator or his designee will maintain the trial drug inventory using an accountability form containing the following information:

- Identification of the subject for whom the drug was dispensed.
- Treatment number, date and quantity of the drug dispensed to the subject and identification of the person dispensing drug.
- Date(s) and quantity of the drug returned as not administered to the subject (if applicable) and identification of the person in receipt of the drug.
- Documentation of any wasted/broken units, including reason and disposition.

Returned study drug must not be administered to another subject. The study drug inventory will be available for periodic inspection/verification.

At the end of the study all unused study drug and placebo will be disposed of appropriately in accordance with study protocol and any institutional Standard Operating Procedures. Reconciliation of shipped, dispensed, and remaining drug will be performed. Any discrepancies noted will be investigated, resolved, and documented.

7 STUDY PROCEDURES

7.1 Duration of Study Drug Treatment

The duration of study drug treatment will be for one dose for Part A and for 4 weeks for Part B. All subjects in Part B will receive a total of 84 doses.

7.2 Duration of Study

Eligibility of subjects for enrollment will be based on the results of screening for inclusion and exclusion criteria. Screening will occur up to 30 days prior to initiation of study treatment. Each subject will continue in the study for 4 weeks (±1 week) after last dose of study drug. The study will be carried out at one site. Enrollment for this trial will occur over a period of 2-3 months with a total of 20 enrolled subjects.

7.3 Screening

Evaluation for eligibility for enrollment will be performed in healthy volunteers at the study site. Screening evaluations must be conducted within 30 days of initiating study drug on Day 1 and will consist of:

- Written informed consent from subject prior to study assessments or procedures
- Screen for inclusion/exclusion criteria
- Medical/surgical history and documentation of comorbidities
- Record concomitant medications

- Record height and weight
- Physical examination, including vital signs (blood pressure, respiratory rate, heart rate and temperature)
- Serum (beta-hCG) pregnancy test for women of childbearing potential
- Measure hemoglobin, white blood cell count with differential, platelet count, serum PTT, INR, sodium, potassium, calcium, magnesium, phosphate, creatinine, albumin, AST, ALT, alkaline phosphatase, total bilirubin, and eGFR
- Collect serum for HBsAg and HCV screen
- Conduct HIV screen
- Collect urine Drugs of Abuse screen
- Send subject home with stool collection kit for sample to be collected as close as possible to Day 1 before study visit.

7.4 Study Day 1 – Pre-Treatment and Post-Treatment

- Record concomitant medications
- Vital signs (blood pressure, respiratory rate, heart rate and temperature)
- Prior to first study drug administration (up to 4 hours before):
 - Serum or urine (beta-hCG) pregnancy test for women of childbearing potential. The results of this test must be confirmed negative prior to beginning study drug administration.
 - Collect blood for serum to be stored for baseline pharmacokinetics
 - Collect blood for serum to be stored for baseline anti-drug antibodies
 - Collect urine Drugs of Abuse screen
 - Obtain baseline stool specimen collected by subject (if subject is unable to produce a void, they are still eligible to be admitted to the study)
- Part B only: Supply one-week supply of study drug to subject (except Day 1 first dose)
- Part B only: Instruct subject on self-administration of study drug at home three times daily. The study drug may be taken with meals or liquids. Instruct subject on recording of study drug administration in study drug diary.
- Observe subject self-administer first dose of study drug with 240 mL of water. Subject should be fasting except for water for one hour before and after the first dose only.
- Two hours (± 30 minutes) after administering first dose of study drug:
 Collect blood for serum to be stored for pharmacokinetics
- History and targeted physical exam for assessment and recording of AEs
- Send subject home with stool collection kit for sample to be collected as close as possible to Day 2 before study visit. Time of collection must be recorded.

7.5 Study Day 2

- Record concomitant medications
- Vital signs (blood pressure, respiratory rate, heart rate, and temperature)

- History and targeted physical exam for assessment and recording of AEs.
- Part B only: Review study drug diary with patient and verify study drug compliance with pill count.
- Obtain stool sample collected by subject.
- 24 hours (± 1 hour) after first dose of study drug:
 - Collect blood for serum to be stored for pharmacokinetics
- Part B only: Send subject home with stool collection kit for sample to be collected as close as possible to Day 8 before study visit.

7.6 Study Week 2 (Study Day 8)

- Record concomitant medications
- Vital signs (blood pressure, respiratory rate, heart rate, and temperature)
- Part B only: Collect blood for serum to be stored for pharmacokinetics
- Part B only: Obtain stool sample collected by subject to ship to laboratory.
- Measure hemoglobin, white blood cell count with differential, platelet count, serum PTT, INR, sodium, potassium, calcium, magnesium, phosphate, creatinine, albumin, aspartate aminotransferase (AST), ALT, alkaline phosphatase, total bilirubin, and eGFR
- History and targeted physical exam for assessment and recording of AEs
- Part B only: Review study drug diary with patient and collect returned dosing container to return to pharmacy for quarantine and to verify pill count
- Part B only: Supply one-week supply of study drug to the subject

7.7 Study Week 3 (Study Day 15)

- Record concomitant medications
- Vital signs (blood pressure, respiratory rate, heart rate, and temperature)
- Measure hemoglobin, white blood cell count with differential, platelet count, serum PTT, INR, sodium, potassium, calcium, magnesium, phosphate, creatinine, albumin, AST, ALT, alkaline phosphatase, total bilirubin, and eGFR
- History and targeted physical exam for assessment and recording of AEs
- Part B only: Review study drug diary with patient and collect returned dosing container to return to pharmacy for quarantine and to verify pill count
- Part B only: Supply two-week supply of study drug to the subject.
- Send subject home with stool collection kit for sample to be collected as close as possible to Day 29 (Part A) or Day 28 (Part B) before study visit. Time of collection must be recorded.

7.8 Part B only: Study Week 4 (Study Day 28, Last Day of Study Drug)

- Record concomitant medications
- Vital signs (blood pressure, respiratory rate, heart rate, and temperature)
- Collect blood for serum to be stored for pharmacokinetics

- Collect blood for serum to be stored for anti-drug antibodies
- Measure hemoglobin, white blood cell count with differential, platelet count, serum PTT, INR, sodium, potassium, calcium, magnesium, phosphate, creatinine, albumin, AST, ALT, alkaline phosphatase, total bilirubin, and eGFR
- Serum (beta-hCG) pregnancy test for women of childbearing potential
- Obtain stool sample collected by subject.
- History and targeted physical exam for assessment and recording of AEs
- Review study drug diary with patient and collect returned dosing container to return to pharmacy for quarantine and to verify pill count
- Send subject home with stool collection kit for sample to be collected as close as possible to Day 29 before study visit. Time of collection must be recorded.

7.9 Part A only: Study Week 5 (Study Day 29; 28 days after last dose of study drug ± 4 days)

- Record concomitant medications
- Vital signs (blood pressure, respiratory rate, heart rate, and temperature).
- Collect blood for serum to be stored for anti-drug antibodies
- Measure hemoglobin, white blood cell count with differential, platelet count, serum PTT, INR, sodium, potassium, calcium, magnesium, phosphate, creatinine, albumin, AST, ALT, alkaline phosphatase, total bilirubin, and eGFR
- History and targeted physical exam for assessment and recording of AEs
- Obtain stool sample collected by subject.

7.10 Part B only: Study Week 5 (Study Day 29)

- Part B only: Review study drug diary with patient and verify study drug compliance with pill count.
- Part B only: Collect blood for serum to be stored for pharmacokinetics
- Obtain stool sample collected by subject.

7.11 Part B only: Study Week 8 (28 days after last dose of study drug ± 4 days)

- Record concomitant medications
- Vital signs (blood pressure, respiratory rate, heart rate, and temperature).
- Collect blood for serum to be stored for anti-drug antibodies
- Measure hemoglobin, white blood cell count with differential, platelet count, serum PTT, INR, sodium, potassium, calcium, magnesium, phosphate, creatinine, albumin, AST, ALT, alkaline phosphatase, total bilirubin, and eGFR
- History and targeted physical exam for assessment and recording of AEs

Table 3: Schedule of Evaluations Part A

	Screening	Week 1		Week 2	Week 3	Week 4 End of Study
		Day 1	Day 2	Day 8	Day 15	Day 29 ¹
Informed Consent	Х					
Inclusion/Exclusion Criteria	Х					
Medical/Surgical History, Comorbidities	Х					
Record concomitant medications	Х	Х	Х	Х	Х	х
Pregnancy test ²	Х	Х				
Physical Examination	Х					
Vital Signs	Х	х	Х	Х	Х	х
Height/Weight	Х					
Collect serum for pharmacokinetics ³		XX	Х			
Collect serum for anti-drug antibodies		Х				Х
Collect blood for hematology ⁴	Х	X ⁷		Х	Х	Х
Collect serum for chemistry ⁵	Х	X ⁷		Х	Х	Х
Collect blood for coagulation ⁶	Х	X ⁷		Х	Х	Х
Collect serum for HBsAg, HCV screen	Х					
Collect serum for HIV screen	Х					
Collect urine for Drugs of Abuse screen	Х					
Obtain stool sample		Х	Х			Х
Administer study drug (single dose)		x				
History & targeted physical exam for AEs		Х	X	X	X	X

¹ Follow-up at Day 29 (28 days after last dose of study drug ± 4 days) for assessment of adverse events, and blood sampling, including anti-drug antibody and clinical laboratory studies.

² Serum beta-hCG pregnancy test from women of childbearing potential at screening. Repeat serum or urine pregnancy test on Day 1.

³ Serum PK before, and 2 hours and 24 hours (Day 2) after administering first dose of study drug (Day 1). This consists of 3 total samples per subject.

⁴ Hematology to include hemoglobin, white blood cell count with differential, and platelet count.

⁵ Serum chemistry to include sodium, potassium, calcium, magnesium, phosphate, creatinine, albumin, AST, ALT, alkaline phosphatase, total bilirubin, and eGFR.

⁶ Coagulation to include PTT and INR.

⁷ Hematology, chemistry and coagulation studies only need to be performed if screening blood tests were performed more than 2 weeks prior to baseline visit.

Page 30

Table 4 Schedule of Evaluations Part B

	Screening	Week 1		Week 2	Week 3	Week 4	Week 5	End of Study
		Day 1	Day 2	Day 8	Day 15	Day 28	Day 29	Day 56 ⁸
Informed Consent	Х							
Inclusion/Exclusion Criteria	Х							
Medical/Surgical History, Comorbidities	Х							
Record concomitant medications	Х	Х	Х	х	Х	Х		Х
Pregnancy test ⁹	Х	Х				Х		
Physical Examination	Х							
Vital Signs	Х	Х	Х	Х	Х	Х		Х
Height/Weight	Х							
Collect serum for pharmacokinetics ¹⁰		XX	Х	х		Х	Х	
Collect serum for anti-drug antibodies		Х				Х		Х
Collect blood for hematology ¹¹	Х	X ¹⁴		Х	х	Х		Х
Collect serum for chemistry ¹²	Х	X ¹⁴		Х	Х	Х		Х
Collect blood for coagulation ¹³	Х	X ¹⁴		Х	Х	Х		Х
Collect serum for HBsAg, HCV screen	Х							
Collect serum for HIV screen	Х							
Collect urine for Drugs of Abuse screen	Х							
Obtain stool sample		Х	Х	Х		Х	Х	
Administer study drug (first dose) ¹⁵		Х						
Administer study drug po TID daily for 28 days		Х	Х	Х	Х	Х		
History & targeted physical exam for AEs		Х	Х	Х	Х	Х		Х
Verification of dosing by diary, pill count			Х	Х	Х	Х	Х	

⁸ Follow-up at Day 56 (28 days after last dose of study drug ± 4 days) for assessment of adverse events, and blood sampling, including anti-drug antibody and clinical laboratory studies.

⁹ Serum beta-hCG pregnancy test from women of childbearing potential at screening and end of dosing. Repeat serum or urine pregnancy test on Day 1.

¹⁰ Serum PK before, and 2 hours and 24 hours (Day 2) after administering first dose of study drug (Day 1); Day 8; on last day of study drug (Day 28) and on the day following the last dose of study drug (Day 29). This consists of 6 total samples per subject.

¹¹ Hematology to include hemoglobin, white blood cell count with differential, and platelet count.

¹² Serum chemistry to include sodium, potassium, calcium, magnesium, phosphate, creatinine, albumin, AST, ALT, alkaline phosphatase, total bilirubin, and eGFR.

¹³ Coagulation to include PTT and INR.

¹⁴ Hematology, chemistry and coagulation studies only need to be performed if screening blood tests were performed more than 2 weeks prior to baseline visit.

¹⁵ Two subsequent doses for Day 1 are to be self-administered by subject out of the clinic.

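### Part B participants attend on Day 29, the day after the last dose, with no scheduled adverse-event or concomitant-medication enquiry; adding one is a cheap, minor improvement

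*Protocol*

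**What the plan says.** The Protocol section headed "7.10 Part B only: Study Week 5 (Study Day 29" gives this visit three activities. Staff go over the dosing diary and count the pills, they draw a PK sample ("Part B only: Collect blood for serum to be stored for pharmacokinetics"), and they take in a stool specimen. Table 4 marks the same three in its Day 29 column and leaves the rows for AE history with targeted examination, concomitant medications and vital signs blank.

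Participants do attend. Blood is drawn, and 7.8 sends them home on Day 28 with a stool kit to use before the Day 29 visit. Footnote 10 of Table 4 places the last two PK samples "on last day of study drug (Day 28) and on the day following the last dose of study drug (Day 29".

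The visits on either side are fuller. Section 7.8 (Day 28, the last dosing day) has an AE history with targeted examination, concomitant medications, vital signs and laboratory tests. The next visit with those items is headed "7.11 Part B only: Study Week 8 (28 days after last dose of study drug ± 4 days", shown as Day 56 in Table 4.

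The SAP matches the protocol. The Part B rows of the vital-signs, hematology and chemistry shells (Tables 14.3.4.4.1, 14.3.4.1.1 and 14.3.4.2.1) go from Day 28 to Day 56. SAP Table 14.1.4 does have a Day 28 to Day 29 compliance interval.

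**The concern.** Dosing is three times daily through Day 28, and the plan verifies dosing again on Day 29. It therefore allows for doses taken after the Day 28 visit. On Day 29 staff check whether those doses were taken, but no scheduled item asks how they were tolerated.

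After the first dose the plan does more: on Day 2, about 24 hours later, 7.5 schedules concomitant medications, vital signs and "History and targeted physical exam for assessment and recording of AEs". The subject diary is described in 6.4 as a place "to record study drug administration, date, time, and relationship to meals", with no mention of symptoms.

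Safety and tolerability is the primary endpoint, and each Part B dose has only four active participants, so one participant is 25% of a dose group (1/4). Section 8.3 asks for onset and resolution by date and time, and for causality, for every AE. A mild, short-lived event after the final doses may be forgotten or poorly dated if the first question about it comes about four weeks later.

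**Working it through.** **Inputs.** Three doses a day for 28 days (Protocol 6.2); 84 doses in total (7.1); Day 28 is the last dosing day (7.8); follow-up is 28 days after the last dose, ±4 days (7.11 and Table 4 footnote 8) or ±1 week (Protocol 4.1 and 7.2, SAP 2.1). Scheduled Part B AE enquiries fall on Days 1, 2, 8, 15, 28 and 56 (Table 4).

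**Reproducing the plan's figures.** 3 × 28 = 84 doses, as stated. 28 + 28 = Day 56, as stated.

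**Doses not covered by the Day 28 enquiry.** By the end of Day 27, 3 × 27 = 81 doses are due. Day 28 adds 3. The visit time is not given, so 81 to 84 doses precede the enquiry and 0 to 3 follow it.

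**Time from Day 28 to the next scheduled AE enquiry.**

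| Follow-up window | Visit falls on | Days after Day 28 | Days after Day 29 |
|---|---|---|---|
| Nominal | Day 56 | 28 | 27 |
| ±4 days | Days 52–60 | 24–32 | 23–31 |
| ±1 week | Days 49–63 | 21–35 | 20–34 |

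**Gaps between successive scheduled AE enquiries.**

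- As planned: 2−1, 8−2, 15−8, 28−15, 56−28 = 1, 6, 7, 13, 28 days.
- With an enquiry on Day 29: 1, 6, 7, 13, 1, 27 days.

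The addition cuts the longest gap by only one day, from 28 to 27. Its value lies in where the enquiry falls: after every dose has been taken and about a day after dosing stops.

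**The case against.** The case against giving this much weight is strong, and most of it stands.

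- **AE capture is not switched off.** A reader might infer that there is no safety contact from Day 28 to Day 56. The documents do not support that. Staff see the participant on Day 29. Section 8.3 requires AEs that are volunteered, given in reply to an open question or observed to be recorded until the end of the study. Section 7.12 requires reported medications to be recorded, and 8.1 and 8.4 cover serious AEs for 28 days after treatment. Section 7.16 promises frequent AE assessment, though it names no day. Only the scheduled prompt is missing.
- **The long interval remains.** A reader might take the 24 to 32 days as the harm that a Day 29 enquiry removes. It does not: about 27 days still follow Day 29.
- **Escalation.** A reader might infer that cohorts are escalated without AE data from after dosing. Sections 4.1 and 4.3 require a review between cohorts but set no date or data cut-off. The 2–3 month enrollment forecast in 7.2 hints at reviews before follow-up is complete. If each cohort started on one day and both reviews waited for a Day 49 visit (48 days after the first dose), cohort 3 would start 2 × 48 = 96 days after cohort 1, against about 92 days in three months. That is a forecast set against an assumed pattern, not a review rule.
- **The Day 2 comparison is imperfect.** Day 2 follows the first dose of a product new to humans. By Day 29 there have been five scheduled AE enquiries, and systemic absorption is not expected (2.1 and 7.19).
- **Vital signs.** Recall and onset dating have nothing to do with vital signs, so their absence on Day 29 is not part of the problem.
- **The diary.** Section 6.4 describes its content, but the form itself and the Study Manual are not among the documents. It cannot be said with certainty that nothing prompts recall.

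What survives is narrow: no scheduled question covers any late Day 28 doses and the first day off drug, although the participant is in the clinic.

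**Conclusion.** The point holds as a minor improvement. The protocol text, Table 4 and the SAP shells agree with one another, so this is a design choice and not a contradiction. All 18 Part B participants are affected. For each, 0 to 3 of 84 doses and the first day off drug have no prompted AE enquiry until about Day 56: 24 to 32 days after Day 28 with the ±4-day window, 21 to 35 with the ±1-week window. The dose count rests on the unstated time of the Day 28 visit. If every participant took all three doses before that visit, only the first day off drug would be at issue.

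The documents do not show that any event would be lost, that an escalation decision would be made on poorer data, or that the post-dosing interval as a whole would be repaired by this change.

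**What to change.** Add two items to Protocol 7.10 and mark them in the Day 29 column of Table 4:

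1. "History and targeted physical exam for assessment and recording of AEs", as at the other visits.
2. The recording of concomitant medications, as at the other visits.

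The SAP's AE and concomitant-medication tables are not laid out by visit, so they need no change. Vital signs are optional. If they are added, Table 4 needs a third mark and the Part B vital-signs shells need a Day 29 row (Table 14.3.4.4.1, both its change-from-baseline and change-from-follow-up layouts, and the shift Tables 14.3.4.4.2 and 14.3.4.4.3).

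The cost is two lines and two table marks, plus staff time at a visit that already takes place. A few minutes for each of 18 participants is an assumption; the documents give no figure. No new visit or blood draw is needed.

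Separately, the two follow-up windows (±4 days in 7.11 and Table 4; ±1 week in Protocol 4.1 and 7.2 and SAP 2.1) must be reconciled. Whether to schedule any contact between Day 29 and Day 56 is a different question, which this change leaves open.
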